- Uncontrolled Diabetes
- Recent (e.g 1year) arterial thrombotic events (peripheral arterial disease, thrombotic stroke)
- Clinically significant arrhythmias requiring anti-arrhythmic agent(s) or conduction abnormalities that in the opinion of the investigator that affect patient safety such as the abnormalities listed below (patients with stable coronary artery disease are eligible)
 - ♦ Angina symptoms
 - ♦ History of MI
 - ♦ Revascularization procedure in the last year prior to screening
 - ♦ Clinically significant congestive heart failure (known LVEF $\leq 45\%$, cor pulmonale, diastolic heart failure, etc)

Investigational Drug: Ivacaftor, 150 mg PO every 12 hrs (or matching placebo)

Schedule of Study Visits: The first dose of ivacaftor will be administered at the Day 1 visit. Ivacaftor will be taken twice daily, with 12 hours between each dose from day 1 through the morning dose of day 84. Study visits will occur at Screening (-28 to -1 days), Day 1, Day 28 (\pm 7), Day 56 (\pm 7), Day 84 (\pm 7), and Follow-up (14 \pm 7 days after the last dose of ivacaftor).

Outcome Measures:

Safety assessments: Assessments include tests used in clinical studies to monitor the safety of ivacaftor in CF, including adverse event reporting, clinical laboratory testing, physical exams, and spirometry. The PI will review all SAEs in real time and conduct appropriate reporting to the FDA and IRB, as required, within 24hrs at maximum. Interim safety analysis will include review of AEs and safety labs by the PI and will be conducted after completion of approximately 10, 20, and 30 subjects. Ocular exam will be performed at baseline unless known history of cataracts.

PK: PK/PD analyses between ivacaftor levels and CFTR activity in the sweat gland will reveal new insights into the degree that wild-type CFTR can be activated. Calculated PK parameters include: area-under-the-curve (AUC₁₂), maximum plasma concentration (C_{max}), time to C_{max} (T_{max}), oral clearance (CL/F), terminal apparent distribution volume (V_z/F), and elimination half-life (t_{1/2}). Subsequently, intensive data and sparse plasma concentrations will be combined to create a population PK model to assess covariates, such as age, weight, sex, smoking status, etc. as previously conducted by our group for NIH and industry sponsored studies.

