5.0 SELECTION OF STUDY POPULATION

Inclusion Criteria:

- Male or Female age 40-80
- A Clinical diagnosis of COPD as defined by GOLD
- At Least a 10 pack year smoking history
- Exhibit symptoms of chronic bronchitis as defined by the Medical Research Council
- FEV1% predicted \geq 35% and \leq 70% Post Bronchodilator
- Clinically stable in the last 4 weeks with no evidence of COPD exacerbation
- Weight of 40 kg-120 kg
- Willingness to use at least one form of acceptable birth control including abstinence, condom with spermicide, or hormonal contraceptives from time of signing ICF through study follow up visit
- Willing to monitor blood glucose if known history of diabetes mellitus requiring insulin or medical therapy
- Element of CFTR Dysfunction, as defined by Sweat Chloride $>$ 30 mEq/L

Exclusion Criteria

- Current Diagnosis of Asthma
- Known Diagnosis of Cystic Fibrosis
- Daytime use of Oxygen Therapy
- Documented history of drug abuse within the last year
- Subjects should not have a pulmonary exacerbation or changes in therapy for pulmonary disease within 28 days before receiving the first dose of study drug.
- Cirrhosis or elevated liver transaminases $>$ 3X ULN
- GFR $<$ 50 estimated by Cockroft-Gault
- Any illness or abnormal lab finding that, in the opinion of the investigator might confound the results of the study or pose an additional risk in administering study drug to the subject.
- Pregnant or Breastfeeding
- Subjects taking moderate or strong inhibitors or inducers of CYP3A4, including certain herbal medications and grapefruit juice. (Excluded medications and foods including the drugs and foods listed in the IRB HSP application.)
- Uncontrolled Diabetes
- Recent (e.g 1year) arterial thrombotic events (peripheral arterial disease, thrombotic stroke)

- Clinically significant arrhythmias requiring anti-arrhythmic agent(s) or conduction abnormalities that in the opinion of the investigator that affect patient safety such as the abnormalities listed below (patients with stable coronary artery disease are eligible)
 - ♦Angina symptoms
 - ♦History of MI
 - ♦Revascularization procedure in the last year prior to screening
 - ♦Clinically significant congestive heart failure (known LVEF $\leq 45\%$, cor pulmonale, diastolic heart failure, etc)

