6.0 Statistical Analysis Plan

Safety analysis will be conducted by descriptive statistics. Pharmacodynamic analysis will be evaluated within group for the ivacaftor treatment group for changes between screening/day 1 and day 84. We will also compare findings between groups. The primary outcome measure is safety; the primary efficacy outcome measure is MCC (AUC₆₀) and change in FEV1 (% predicted). Secondary outcome measures including change in other measures of spirometry, PROs, exacerbation frequency, and 6MWD will also be analyzed. These data will be used to test the null hypothesis of no change using a paired t-test unless the distributions are notably skewed, in which case the non-parametric Wilcoxon signed-rank test will be implemented. Between group comparisons and composite time-dependent changes based on multiple measures (e.g. sweat chloride, MCC, FEV1, etc.) will be conducted as secondary analyses using the two-group t-test (or the non-parametric Wilcoxon rank-sum test if needed) and analysis of covariance models. The dose groups will be compared simultaneously using analysis of variance (or the nonparametric Kruskal-Wallis test if needed). Longitudinal analyses will consist primarily of mixed models repeated measures analyses. An appropriate structure for the covariance matrix will be selected for these models using the final data. When a model term is statistically significant, the Tukey-Kramer multiple comparisons test will be used to determine which specific pairs of means are significantly different. Interaction terms may be included in some models. All statistical tests will be two-sided and will use $\alpha=0.05$. Power analysis for measurements of MCC, CFTR function measured by sweat chloride, and FEV1 (% predicted) are provided below. The off drug effect will be measured by using data from the follow-up visit to assess the change from on drug to washout at the follow up visit.

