16.8 Elevation of Liver Function Test Parameters

Subjects with new ALT or AST elevations of $>3 \times$ ULN and clinical symptoms be followed closely, including repeat confirmatory testing within 48 to 72 hours of the initial finding and subsequent close monitoring of ALT and AST level, as clinically indicated.

Study drug administration will be interrupted immediately and the DSMB Chair will be notified if any of the following criteria is met:

- ALT or AST $>8 \times$ ULN
- ALT or AST $>5 \times$ ULN for more than 2 weeks
- Total bilirubin $>2 \times$ ULN and/or clinical jaundice, in association with elevation of ALT or AST $>3 \times$ ULN

A thorough investigation of potential causes should be conducted and the subject will be followed closely for clinical progression.

If no convincing alternative etiology (e.g., viral hepatitis, alcohol ingestion) for the elevated transaminases is identified, regardless of whether ALT or AST levels have improved, the subject will be discontinued from the study, in consultation with the Medical Monitor

An early termination visit should be scheduled as soon as possible. In addition to the early termination visit assessments specified in the protocol, a blood sample should be obtained for pharmacokinetic analysis. Subjects discontinued for elevated transaminases should be followed until their transaminases normalize or return to baseline. If a convincing alternative etiology for the elevated transaminases is identified and the subject's symptoms and laboratory findings have improved, the investigator will consider resuming study drug treatment in consultation with the PI.

16.9 Definition of COPD Exacerbation.

We will monitor the incidence and severity of COPD exacerbations to measure safety of ivacaftor and estimate whether a reduction in COPD exacerbations is plausible with effective CFTR potentiation by ivacaftor, and to develop sample size estimates for future studies. For the purposes of this protocol, COPD exacerbations will be defined as follows: a complex of respiratory symptoms (increase or new onset) of more than one of the following: cough, sputum, wheezing, dyspnea, or chest tightness, requiring treatment with antibiotics and/or systemic steroids for at least three days.

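### Section 6.0 tests exacerbation frequency for no change by a paired test but defines no pre-treatment counting period; on the only baseline it describes, eligibility makes every count zero

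*Combined protocol and SAP*

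**What the plan says.** Section 6.0 (Statistical Analysis Plan) groups exacerbation frequency with outcomes that are measured at visits: "Secondary outcome measures including change in other measures of spirometry, PROs, exacerbation frequency, and 6MWD will also be analyzed". The next sentence applies to the whole list: "These data will be used to test the null hypothesis of no change using a paired t-test unless the distributions are notably skewed". For skewed data the plan switches to a signed-rank test. No exception is made for event counts.

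The only within-group interval in Section 6.0 is the one given for the pharmacodynamic analysis: "within group for the ivacaftor treatment group for changes between screening/day 1 and day 84". The Synopsis fixes where that baseline lies: "Study visits will occur at Screening (-28 to -1 days), Day 1".

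Section 5.0 restricts the same period twice. An inclusion criterion reads "Clinically stable in the last 4 weeks with no evidence of COPD exacerbation". An exclusion criterion reads "Subjects should not have a pulmonary exacerbation or changes in therapy for pulmonary disease within 28 days before receiving the first dose".

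Section 16.9 defines an exacerbation by symptoms and treatment. It gives neither a counting period nor a baseline period. Among its purposes for these data is to "estimate whether a reduction in COPD exacerbations is plausible with effective CFTR potentiation by ivacaftor"; the others are to measure safety and to support sample sizes for later studies.

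Section 6.0 also plans between-group comparisons, as secondary analyses, by two-group t-test or rank-sum test.

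**The concern.** A paired test of no change needs a baseline that could lie above or below the on-treatment value. Spirometry and walk distance have one. Exacerbation frequency has one only if a pre-treatment period is chosen, and the plan chooses none. If the analyst uses the baseline that Section 6.0 describes, every prior count is zero by selection. Expressing counts as rates does not help, because zero events in 28 days is still a rate of zero.

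Two things follow. No patient can show a decrease, so the test cannot address the reduction that Section 16.9 asks about. And no change is the wrong null for an inert drug, since untreated patients with COPD also exacerbate over 84 days. The result could be a p-value pointing to harm, in a trial whose primary outcome is safety, that comes from the entry criteria and not from ivacaftor.

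**Working it through.** **Inputs from the documents.** Treatment lasts 84 days and 30 patients are planned on ivacaftor and 10 on placebo (Section 4.0). The paired test has n = 27 after 10% drop-out (Table 2 caption). Tests are two-sided at 0.05 (Section 6.0), so the nominal error is 2.5% in each direction. **Assumed:** background rates of 0.25 to 1.5 exacerbations per year, because the documents give none.

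**Plan's own figures.** No power or rate is stated for exacerbations. As a check on the test itself, Table 2 was recomputed. Power is P(T > 2.056), where T is noncentral t with 26 df and noncentrality δ√27/SD. The detectable differences at 80% / 90% power are:
- MCC (SD 7): 3.92 / 4.54; the plan has 3.9 / 4.5.
- FEV1 (SD 5): 2.80 / 3.24; the plan has 2.8 / 3.2.
- Sweat chloride (SD 4): 2.24 / 2.59; the plan has 2.3 / 2.6.

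The table reproduces apart from rounding.

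**How few events are needed when every baseline is zero (n = 27).**
- Paired t, four patients with one event each: mean 4/27 = 0.148, SD 0.362, t = 0.148/(0.362/√27) = 2.13, p = 0.043. With three patients, p = 0.083.
- Exact signed-rank, zeros dropped and k positive changes: p = 2/2^k. Five patients give 0.0625 and six give 0.031, so six are needed. With the tied normal approximation, four patients with one event each already give p = 0.0455.

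**Chance of a significant increase with an inert drug.** The expected count per patient is λ = rate × 84/365.25, which is 0.115, 0.230 and 0.345 at 0.5, 1.0 and 1.5 per year.
- For the exact signed-rank test the chance is P(at least 6 of n patients have an event). The per-patient probability is 1 − e^(−λ) = 0.109, 0.205, 0.292 under Poisson, and λ/(1+λ) = 0.103, 0.187, 0.256 with overdispersion k = 1.
- The paired t-test was simulated with at least 40,000 trials per cell.

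Ranges run from n = 27 to n = 30:

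| Test | 0.5/yr | 1.0/yr | 1.5/yr |
|---|---|---|---|
| Paired t, Poisson | 30–37% | 77–84% | 95–97% |
| Paired t, k = 1 | 24–31% | 65–74% | 86–92% |
| Exact signed-rank, Poisson | 7–10% | 49–60% | 84–91% |
| Exact signed-rank, k = 1 | 5–8% | 39–50% | 73–82% |

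At 0.25 per year under Poisson the figures are about 5–8% (paired t) and below 1% (exact signed-rank). The chance of a significant decrease is zero throughout.

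**Other baselines (paired t, n = 27, Poisson, rates 0.5 to 1.5).**
- Annualised 12-month history with the last 28 days empty: false increase 1–2%, false decrease 3–6%.
- 84-day look-back with the last 28 days empty: false increase 5–10%, false decrease below 1%.
- 84-day look-back without the eligibility restriction: about 2.1–2.5% in each direction.

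**Randomised comparison.** The two-group t-test with 27 v 9 and an inert drug has two-sided type I error of 3.0%, 3.7% and 4.8% at 0.5, 1.0 and 1.5 per year.

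**Precision of a rate ratio at 1.0 per year.** Expected events are 30 × 0.230 = 6.9 and 10 × 0.230 = 2.3, say 7 v 2. The exact binomial 95% interval for 7/9 is 0.400 to 0.972. Converting by [p/(1−p)]/3 gives a rate ratio interval of 0.22 to 11.5.

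**The case against.** **The zero baseline is not stated for this outcome.** The screening/day 1 contrast is given for the pharmacodynamic analysis, and no section says that exacerbations will be counted over the 28-day eligibility window. A reader might infer that eligibility forces the whole pre-treatment count to zero. It does not: it fixes only the last 28 days. Medical history is taken at screening (Table 1), and a 12-month look-back would largely remove or mildly reverse the bias. This stands as a limit on the claim. It does not rescue the text, because no look-back is defined and the direction of the bias is left to a later choice.

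**The t-test figures may not be the operative ones.** Mostly-zero counts are skewed, so the plan's own rule would probably select the signed-rank test, which is less inflated. A reader might infer that the trial will usually report a harmful increase. The documents do not support that. They give no rate; at 0.5 per year such a result is the exception under either test, and at 1.0 per year the exact signed-rank test is near an even chance. The bias nevertheless keeps its direction under both tests.

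**A valid comparison is already planned.** The between-group analysis does not share this bias and its type I error is controlled. This stands. It is, however, placed second to the paired test, and a test on raw counts takes no account of follow-up time. Section 9.1 allows for 5 drop-outs of 35 on ivacaftor (14%) and 5 of 15 on placebo (33%), so exposure could differ by arm.

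**Little rests on the p-value.** Safety is analysed descriptively, Section 16.9 speaks of monitoring and estimating, and no decision rule uses the paired test. This stands, and it limits the seriousness of the point.

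**Conclusion.** The concern holds in a limited form. As written, Section 6.0 applies a paired no-change test to exacerbation frequency without a defined baseline period. On the only within-group baseline it describes, the test cannot show a reduction, whatever the background rate. It also favours a false increase by an amount that depends on that rate: slight at 0.25 per year, and more likely than not above roughly 0.7 per year (paired t) or 1.0 per year (exact signed-rank) with Poisson counts and n = 27. These sizes rest on assumed rates, 84 days of full follow-up and an all-zero baseline.

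This should be fixed, but it does not threaten the trial's main conclusions. The outcome is one unpowered secondary measure in a pilot, and the safety, PK, MCC and FEV1 analyses are unaffected.

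**What to change.** In Section 6.0, take exacerbation frequency out of the paired-test sentence and add, in substance:

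- Events meeting the Section 16.9 definition are counted from first dose over a stated period, for example to day 84 or to the follow-up visit.
- The analysis for this outcome is the randomised ivacaftor v placebo comparison, already planned as a secondary analysis. It is expressed as events per patient-year with follow-up time as exposure, with an exact conditional 95% interval for the rate ratio, and is labelled estimation only.
- Counts, patient-years and rates are reported descriptively by arm.

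The cost is a few sentences in the SAP and a few lines of code, with no new data or visits. The drawback is a wide interval, about 0.22 to 11.5 for 7 v 2 events. A dispersion estimate from about nine events should not be relied on for planning later studies.

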6.1 Power and Sample Size Calculations

The size of the study was chosen based on the ability to detect a meaningful within subject change in MCC and FEV1, while also providing a study population suitable to detect safety signals and determine clinical and physiologic outcome measures for future studies. The sample size was calculated for the target population (e.g. those with chronic bronchitis, which is associated with CFTR dysfunction¹³⁻¹⁶) based on prior experience with the CFTR endpoints and our knowledge of anticipated activity of ivacaftor in CF airway epithelia, which is substantiated based on the close relationship between CFTR activity *in vitro* and potential difference findings *in vivo* in CF subjects.¹⁷⁻²⁵ Choice of endpoints and sample size have also been informed by the pilot study.¹² Based on experience with ivacaftor using MCC imaging²⁶, and our preliminary data demonstrating sweat test abnormalities among COPD smokers (including repeated measures), our study also has sufficient power to detect changes in these parameters.^{27,28} Although we do not have sufficient data from the Pilot Study to perform an estimated sample size for changes in FEV1 with ivacaftor, we know from prior experience in COPD the variance of FEV1 in populations of this sort. Sample size calculations for key primary and secondary endpoints are shown in Table 2.

	Power based on response magnitude of	Within-
--	--------------------------------------	---------

Assay (unit)	Detectable difference		50% of the difference between COPD and normal		subject reproducibility (SD)
	80% Power	90% Power	Efficacy	Power	
MCC (AUC _{60 min})	3.9%	4.5%			7% ^{29,30}
Spirometry (FEV ₁) ^d	2.8% ^b	3.2%			5% ³¹
Sweat Chloride (mmol/L)	2.3	2.6	9.9 mmol/L	>99% ^a	4 mmol/L ^{18,32}

Table 2. Power and sample size of the proposed study. All calculations are based on within subject changes observed with prior experience (as indicated by references in Table) or preliminary data, n=27 active treatment patients among all doses assignments and accounting for 10% drop-out rate, a two-sided paired t-test, and $\alpha=0.05$. ^aPower=80% between-groups at SD=12.8 mmol/L and 90% at SD=11.1 mmol/L. ^bPower=80% to detect 3.9% change in FEV₁% between groups; this corresponds to 5.1% relative improvement in FEV₁ assuming ~55% FEV₁% predicted upon enrollment, a typical mean value for COPD studies at our center with similar enrollment criteria. These two between-group calculations (a and b) assume a two-sided two-group t test. ^cThis is a conservative estimate based on extensive experience in NPD; within group SD is < 3 at our center. ^dBased on experience testing ivacaftor in CF patients, LCI exhibits even greater power than spirometry, so we have an excellent sample size to detect a meaningful effect.²⁸

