4.0 STUDY DESIGN

The study is a Phase 2 Study to establish the safety and efficacy of the CFTR potentiator ivacaftor in patients with chronic obstructive pulmonary disease (COPD), chronic bronchitis, and acquired CFTR dysfunction as detected by sweat chloride analysis. The design is a pilot, randomized (3:1, active:placebo), double-blind, placebo-controlled study to determine the safety and efficacy of ivacaftor (VX-770) in approximately 40 subjects with COPD.

Enrollment is planned at our single center, The University of Alabama at Birmingham. Patients will be randomized 3:1 to active drug (n=30) and placebo (10) to achieve the enrollment goal.

- A sufficient number of subjects will be screened to randomize up to 50 subjects to achieve 40 completed subjects to receive either ivacaftor 150 mg BID (n=30) or placebo (n=10) for 84 days.
- The schedule of assessments is shown in Table 1. The protocol design is shown in Figure 1.
- Ivacaftor and matching placebo will be orally administered as capsules according to the following guidelines:
 - Between study visit Day 1 and study visit Day 84, subjects will take 1 dose of study drug each day in the morning, beginning any time between 08:00 h (8:00 AM) and 12:00 h (12:00 PM). Whenever possible, subjects should take the study drug at the same time each day.

- On the study visit days when PK samples are collected (study visit Days 1, 28, 56, and 84), the study drug is to be taken by the subject while he/she is at the study site
- For visits after the Day 1 visit, subjects will be instructed to bring all remaining study drug materials to the site; study drug will be dispensed at each visit.
- Ivacaftor will be prepared and dispensed by an unblinded pharmacist.
- Subjects will be instructed to continue their standard COPD medication regimen.

Table 1. Schedule of Assessments ^a8 hr PK (pre, 1, 2, 4, 8, hr samples). ^b peak and trough PK only, ^crandom PK, ^donly if indicated.

Assessment	Screen (Day -28 to -1) Visit 1	Day 1	Day 28 (± 2)	Day 56 (± 2)	Day 84 (± 2)	Follow Up (Day 98 ± 2)
		Visit 2	Visit 3	Visit 4	Visit 5	Visit 6
Informed Consent	X					
Medical History & Concomitant Medications	X	X	X	X	X	X
Physical Examination	X	X	X	X	X	X
Safety Labs	X		X	X	X	X ^d
CFTR Genotyping	X					
Urine Pregnancy Test		X	X	X	X	X
Serum Pregnancy Test	X					
Blood Biomarker Collection		X	X	X	X	X
Spirometry	X	X	X	X	X	X
Sweat Chloride	X	X	X	X	X	X
MCC	X				X	
Patient report outcome questionnaires		X	X	X	X	X

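### Table 2 footnotes a and b claim between-group power that 30 v 10 patients do not give: about 50–55%, not 80%, for 3.9 FEV1% points (SD 5), which is 7.1% relative, not 5.1%

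*Combined protocol and SAP*

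**What the plan says.** Section 4.0 fixes the design: "Patients will be randomized 3:1 to active drug (n=30) and placebo (10) to achieve the enrollment goal". It then plans to randomise up to 50 patients "to achieve 40 completed subjects to receive either ivacaftor 150 mg BID (n=30) or placebo (n=10) for 84 days". The drug-supply text (Synopsis and section 9.1) provides for 35 active and 15 placebo patients, with 5 expected losses in each arm.

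Section 6.1 explains the sample size: "The size of the study was chosen based on the ability to detect a meaningful within subject change in MCC and FEV1". The Table 2 legend bases its calculations on "n=27 active treatment patients among all doses assignments and accounting for 10% drop-out rate" and a paired t-test. Two footnotes then move to the comparison with placebo:

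- Footnote a, attached to the 9.9 mmol/L sweat chloride entry, states power of "80% between-groups at SD=12.8 mmol/L and 90% at SD=11.1 mmol/L".
- Footnote b states 80% power for 3.9 FEV1% points "between groups; this corresponds to 5.1% relative improvement in" FEV1, assuming about 55% predicted at enrolment.

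The legend adds: "These two between-group calculations (a and b) assume a two-sided two-group t test". No placebo n is given. Section 6.0 says that between-group comparisons "will be conducted as secondary analyses using the two-group t-test", a rank-sum test or analysis of covariance.

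**The concern.** The power of a two-group t-test depends on both arms, and the smaller arm dominates. With 10 placebo patients, a between-group detectable difference of 3.9 points looks too close to the paired figure of 2.8 points from 27 patients. The relative-improvement figure also fails a simple division.

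The between-group test is secondary, but it is the only analysis that uses the randomised placebo arm, and change in FEV1 is a named primary efficacy measure. A reader of Table 2 would expect a true 3.9-point benefit over placebo to be found four times in five. If the real chance is about even, a null placebo comparison would be read as stronger evidence against the drug than it is. The figure could also mislead the planning of later trials, which section 6.1 names as one purpose of this study.

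**Working it through.** **Inputs.** Two-sided α = 0.05 (section 6.0) and a two-group t-test (Table 2 legend). FEV1: difference 3.9 points, SD 5 from the spirometry row. Footnote b gives no SD, so using 5 as the SD of change in both arms is an assumption. Sweat chloride: difference 9.9 mmol/L, with footnote a's own SDs of 12.8 and 11.1. Arms: 30 v 10 (section 4.0); 27 v 10 (Table 2's active n with 10 placebo); 27 v 9 (a sensitivity case that applies Table 2's 10% drop-out to placebo too); 35 v 15 (supply text, no drop-out).

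**Formula.** Noncentrality = (difference / SD) × √m, where m = n1·n2/(n1+n2), with n1+n2−2 degrees of freedom. Power comes from the noncentral t distribution.

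**Step 1: reproduce the stated figures.** With 27 per arm, m = 27·27/54 = 13.5. For FEV1, (3.9/5)·√13.5 = 2.87 on 52 df, which gives 80.3%. Sweat chloride gives 79.6% at SD 12.8 and 89.5% at SD 11.1. All three stated figures are matched. Other pairs with m near 13.5 also fit (40 v 20 gives 80.0%, 79.3% and 89.3%), so the use of 27 for both arms is an inference. No arm sizes in the documents have m that large.

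**Step 2: use the planned arms.** At 30 v 10, m = 300/40 = 7.5. For FEV1, (3.9/5)·√7.5 = 2.14 on 38 df, which gives 54.9%.

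| Arms | m | FEV1 3.9, SD 5 | 9.9 mmol/L, SD 12.8 | 9.9 mmol/L, SD 11.1 |
|---|---|---|---|---|
| Stated | – | 80% | 80% | 90% |
| 27 v 27 | 13.5 | 80.3% | 79.6% | 89.5% |
| 35 v 15 | 10.5 | 69.7% | 69.0% | 80.8% |
| 30 v 10 | 7.5 | 54.9% | 54.2% | 66.3% |
| 27 v 10 | 7.3 | 53.6% | 52.9% | 64.9% |
| 27 v 9 | 6.75 | 50.4% | 49.7% | 61.5% |

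**Step 3: invert for what the arms can detect.**

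| Arms | FEV1 difference at 80% power (SD 5) | Relative to 55% | Largest SD for 9.9 mmol/L, 80% / 90% power |
|---|---|---|---|
| 30 v 10 | 5.25 points | 9.5% | 9.4 / 8.1 |
| 27 v 10 | 5.33 points | 9.7% | 9.3 / 8.0 |
| 27 v 9 | 5.55 points | 10.1% | 8.9 / 7.7 |

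(The 90% limit at 30 v 10 is 8.15, rounded down so that power is kept.) For 80% power at 3.9 points, the SD would have to be about 3.7 (30 v 10) or 3.5 (27 v 9). With 30 active patients and SD 5, the placebo arm would need 24 to 25 (79.8% and 80.7%).

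**Step 4: relative improvement.** 3.9/55 = 7.1%. 2.8/55 = 5.1%.

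**Step 5: what is not affected.** With the paired t-test, n = 27 and the tabulated SDs read as SDs of change, Table 2's entries give: MCC 3.9 and 4.5, 79.6% and 89.5%; FEV1 2.8 and 3.2, 80.0% and 89.3%; sweat chloride 2.3 and 2.6, 82.0% and 90.2%. These agree with the stated 80% and 90% to rounding. Between-group power for 9.9 mmol/L at Table 2's SD of 4 exceeds 99.9% even at 27 v 9.

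**The case against.** **Footnote b states no SD.** This is true, and the 50–55% depends on SD 5; at about 3.7 the 30 v 10 arms would reach 80%. But 5 is the only SD in that row and reproduces the stated 3.9 at 27 v 27. Footnote a states its SDs, so the arm-size problem shows there without the assumption.

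**No placebo n of 9 appears in the plan.** This is correct. The figure that rests on section 4.0 is 54.9%; the 27 v 9 values are a sensitivity case.

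**The 5.1% may only be misplaced.** Marker b sits on the 2.8% entry, for which 5.1% is right. That is probably the origin, but the sentence as written attaches it to 3.9 and needs repair either way.

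**The tabulated SD may not be an SD of change.** Its column is headed as within-subject reproducibility. If it describes a single measurement, with independent errors, the SD of change is √2 times larger and paired power for 2.8 points is about 51%. The paired entries therefore hold only on the reading used here. The other reading would make between-group power worse.

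**The consequence is limited.** Between-group tests are secondary, the study is sized on within-subject change, and analysis of covariance might be more precise than the t-test. All of this stands and limits the severity. It does not rescue the footnotes, which name the t-test and give no baseline correlation.

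**The 35/15 supply figure is a ceiling, not a second allocation ratio.** This is largely fair: 35−5 = 30 and 15−5 = 10. Still, 35:15 is 7:3, not the 3:1 stated for randomisation, and one clarifying sentence would settle it.

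**Conclusion.** The concern holds. For the stated test and the planned 30 v 10 completers, power for 3.9 FEV1% points is about 55%, falling to 50% at 27 v 9. Even 35 v 15 with nobody lost gives only 70%. These figures assume an SD of change of 5 in both arms. Footnote a's SDs of 12.8 and 11.1 give 54% and 66% at 30 v 10, not 80% and 90%; the tolerable SDs are lower by about a quarter to a third. The 5.1% belongs to 2.8 points; 3.9 points is 7.1%.

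The practical harm lies in FEV1. The sweat chloride conclusion survives at Table 2's SD of 4, and at an SD of 8 power is still 91% (30 v 10) or 88% (27 v 9). The basis for the sample size does not change. This should be fixed because the plan states a power for its placebo comparison that the design does not have.

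**What to change.** Restate both footnotes with the placebo n and SD shown. Suggested text:

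- **Footnote a:** With 30 v 10 completers, a between-group difference of 9.9 mmol/L is detected with 80% power if the SD of change is at most 9.4 mmol/L, and with 90% power if it is at most 8.1 (8.9 and 7.7 for 27 v 9).
- **Footnote b:** Assuming an SD of change of 5 points in both arms, 30 v 10 completers give 80% between-group power for 5.25 FEV1% points, 9.5% relative at 55% predicted (5.55 points, 10.1%, for 27 v 9). Power for 3.9 points (7.1% relative) is 55% (50% for 27 v 9).

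If the 5.1% is kept, attach it to the 2.8-point within-subject change. State also that the tabulated SDs are SDs of change, if that is what is meant.

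Add one sentence reconciling the counts: 3:1 randomisation against 35:15 supply, and 30 active completers in section 4.0 against 27 active after 10% drop-out in Table 2.

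The cost is two reworded footnotes and a sentence or two. Sample size, tests and the paired calculations stay as they are. The only loss is a less favourable stated power for the placebo comparison of FEV1.
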